6. STUDY MATERIALS

6.1 Investigational Product

6.1.1 Identity of the investigational product

The clinical grade allogeneic MSCs required for this Phase I study will be provided by the Case Western Reserve University in Cleveland, Ohio. MSCs will be cultured from mononuclear cells obtained from a single healthy donor and expanded to passage 2.

6.1.2 Safety issues

Enrolled patients will be randomized to receive 1 or 3 million MSC/kg or placebo IV. This dose has been extrapolated from our preclinical model⁶ and spans the range of MSC doses used in previous clinical trials.⁷⁻¹¹ Hare, et al, tested the safety of allogeneic MSCs in patients with acute myocardial infarction randomized to doses of 0.5, 1.6, and 5 million MSCs/kg in a similar dose escalation study without treatment related adverse events.

6.1.3 Handling, storage, accountability

MSCs will be transported using a liquid nitrogen dry shipper validated for 4 days to maintain temperature for long-term storage. The temperature is logged upon arrival and becomes part of the official shipping documentation. The integrity and temperature of the cell containers are checked on arrival and results documented. The study product should not be at room temperature for more than four hours.

6.1.4 Required training and MSC administration

MSCs will be manufactured at the Case Cancer Comprehensive Center Cellular Therapy Lab at Case Western Reserve University in Cleveland, Ohio with supervised and trained personnel. The MSCs, in the

appropriate dose, will be shipped to the Cell Therapy Laboratory at University Hospital where the MSCs will be thawed and diluted 1:1 with Plasmalyte A and administered within 4 hours of the thawing process. All personnel in the Stem Cell Laboratory are qualified in the processing on MSCs for patient administration. The thawed MSCs will then be administered to the patients in a monitored setting with telemetry and pulse oximetry.

MSC Administration. This is a randomized, double blinded trial and after enrollment, patients will be randomized in a 1:1:1 fashion to receive placebo (Plasmalyte A), 1×10^6 MSC/kg., or 3×10^6 MSC/kg. The rationale for selection of these doses was presented in the Research Strategy. IV MSC infusions will occur in a monitored inpatient room on the Surgical Intensive Care Unit at the Roudebush VA Hospital or the Clinical Research Center at IU Health University Hospital. Patients will be pre-medicated with hydrocortisone (25-50 mg. IV) and diphenhydramine (Benadryl, 25-50 mg. IV). All subjects will be monitored throughout the MSC infusion procedure with vital signs and pulse oximetry beginning 15 minutes prior to infusion and ending 2 hours post procedure. They will also be evaluated for clinical signs of pulmonary distress including progressive or sustained hypoxia, dyspnea, and tachycardia. If enrolled patients develop any of the following conditions within 24 hours of planned infusion, MSC delivery will be halted:

- a. Fever (Temperature increase to $\geq 100.4^\circ\text{F}$)
- b. Upper respiratory tract infection diagnosed by independent health provider.
- c. Significant shortness of breath
- d. Unanticipated change in consciousness or neurological change
- e. Major adverse cardiac event

All patients will be admitted for continued observation to the SICU at the Roudebush VA Hospital or the Clinical Research Center at IU Health University Hospital. The patient will be observed for two hours after the study product infusion and then discharged home. The patient will be re-examined on Days 7 and 14 for treatment related adverse events.

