7. STUDY PROCEDURES

7.1 Workflow

MSC preparation. Donor infectious disease testing will be performed by CLIA certified Laboratories. Allogeneic donor Infectious Diseases testing will include anti-HIV-1/2 and anti-HCV. Testing will be repeated if it exceeds 30 days. Potential donors whose testing is incomplete or not available within 30 days will not be eligible to donate bone marrow and testing will be repeated to confirm ID markers. Potential donors testing positive for any of these infectious diseases will NOT be eligible.

Randomization Scheme and MSC Dosing. The PI, [name] MD., will determine inclusion in the study. After that decision has been rendered, the patient will be screened for enrollment. After enrollment, 36 patients will be randomized to receive MSCs or placebo IV through an antecubital vein (**Figure 1**).

Serum samples will be collected pre-MSD administration, 1 and 6 months' post MSC-treatment and analyzed in the Cellular Therapy Laboratory of University Hospital to determine if patients develop antibodies against allogeneic MSCs.

Baseline Screening and Follow-Up Schedule. The following evaluations will be carried out at baseline to determine if patient is eligible for study: (1) Baseline blood tests (complete blood count, serum chemistries and liver panel); (2) infectious disease panel and HLA typing; (3) medical history and physical exam; (4) concomitant medications; (5) pregnancy test for women of childbearing age ;(6)12 lead ECG; (7) 18-fluorodeoxyglucose (FDG) uptake with positron emission tomography/computed tomography (PET/CT) will be performed at baseline and Day 14. Computed tomographic angiography of the abdominal aorta and iliac arteries (as part of "Standard of Care") will be performed at month 12. Duplex ultrasound of the aorta will be performed at month 12 while the patients are enrolled in the trial to monitor AAA size. Follow up studies are detailed in **Table 2**, below. Subjects will return for long-term follow-up visits at six month intervals from year 1 (+/- 4 weeks) through year 5 (+/- 4 weeks). Window ranges for follow-up visits are guidelines for scheduling and will not be considered a protocol deviation if visits fall outside of these ranges. See **Table 3**, below, for details on the long-term follow-up visits.

- Annual CT abdominal exams beginning at year 1 are considered Standard of Care.

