- MSCs products will be thawed and diluted 1:1 with Plasmalyte. Samples for cell viability (i.e. Trypan Blue and/or 7AAD) and 14-day bacterial sterility testing will be obtained. Viability >70% will need to be entered in the Certificate of Analysis before the product is released for administration.
- In the event of a positive sterility test result after products infusion, the physician and patient will be informed, and the results reported to the IRB and FDA. The positive result will be reported in an information amendment submitted to the IND in a timely manner, preferably within 30 calendar days after initial receipt of the positive culture test result (21 CFR 312.31).
 - Should cultures for detection of bacteria and fungi become positive, the Principal Investigator of the study will be notified. The PI will then notify the patient and the appropriate antibiotics will be started based on sensitivities of the identified organism.
 - A physical examination of will be conducted within 24 hours at which time a complete blood count will be obtained. Should there be an elevate white blood cell count (> 11.5K), the patient will be admitted to the hospital for intravenous antibiotics or antifungal medications. Should there be no clinical evidence of infection the patient will be treated for 7 days with oral antibiotics or anti-fungal medication
 - A systematic review of potential sources of contamination will be conducted with emphasis on skin preparation and draping and the components of the cell transport and preparation system. An examination of the sterile packaging for disposable components and the process of sterilization of non-disposable components will be performed as part of this review.
 - An infection as a result of contamination will be reported as an adverse event within 15 calendar

Table 2. Follow-Up Schedule

Procedures	Baseline	Day 0 MSC (4-6 hr. visit)⁹	Day 7 F/U (+/- 2 days)	Day 14 F/U (+/- 5 days)	Mo 1 F/U (+/- 1wk)	Mo 6 F/U (+/- 2wk)	Mo 12 F/U (+/-2 wk)	Mo 18 F/U (+/-2 wk)	Mo 24 F/U (+/-4 wk)
Informed Consent	X								
Medical History	X								
Physical Exam	X	X	X	X	X	X			
Vital Signs	X	X	X	X	X	X	X	X	X
Con. Medications	X	X	X	X	X	X	X	X	X
AE/SAE Evaluations	X	X	X	X	X	X	X	X	X
QoL Questionnaires	X					X	X	X	X
Infectious Disease Labs ¹	X								
Laboratory Evaluations	X ²				X ³				
12 Lead ECG	X ⁸				X				
Duplex Ultrasound	X					X	X	X	X
Randomization	X								
PET CT	X			X					
CT Angiogram ⁹							X		X
Blood Sample ⁴		X ⁵	X	X	X	X	X	X	X

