Infusion Reaction Assessment ^{6,7}		X		X					

1. Infectious disease testing including basic HIV, Hepatitis C testing. HLA Typing will be performed at baseline, but is not exclusionary to enrollment, nor a protocol deviation if HLA results after study product infusion.
2. Baseline labs ONLY = CBC with differential, Glucose, Sodium, Potassium, Chloride, CO2, BUN, Creatinine, eGFR, hs-CRP, CPK, HbA1C, Total Bilirubin, Total Protein, Albumin, Alkaline phosphatase, alanine transaminase (ALT), aspartate transaminase (AST), platelet count, PT/INR, Pregnancy (childbearing Females-baseline only).
3. Follow-up labs = CBC with differential, Glucose, Sodium, Potassium, Chloride, CO2, BUN, Creatinine, eGFR, hs-CRP, CPK, Albumin, platelet count.
4. Peripheral blood draw for ancillary studies is up to 34 ml.
5. Day of MSC administration blood sample to be collected prior to study product infusion (can be done at physical exam if within 2 hours of infusion).

6. Infusion reaction assessment will include: clinical observation for signs of tachycardia and cutaneous flushing and vital signs (blood pressure, heart rate, respiratory rate, and temperature) at 15 min intervals throughout infusion starting 15 min prior to infusion. Post infusion vital signs will be monitored at 15 min, 30 min, 1 and 2 hours.
7. Oxygen saturation will be continuously monitored throughout infusion by pulse oximetry starting 15 min prior to infusion through 2 hours post infusion.
8. Baseline ECG may be obtained any time prior to study product infusion.
9. CT Angiograms beginning at year 1 and performed annually throughout subjects' participation are considered Standard of Care.

Table 3. Long-Term Follow-Up Schedule

	Mo 30 (+/-4wks)	Mo 36 (+/-4wks)	Mo 42 (+/-4wks)	Mo 48 (+/-4wks)	Mo 54 (+/-4wks)	Mo 60 (+/-4wks)
Duplex Ultrasound ¹	X	X	X	X	X	X
CT Angiogram ³		X		X		X
QOL Questionnaire	X	X	X	X	X	X
AE/SAE Evaluations	X	X	X	X	X	X
Blood Sample ²	X	X	X	X	X	X

1. Duplex ultrasound measured every six months is considered standard of care.

2. Peripheral blood draw for ancillary studies is 34 ml.

3. CT Angiograms performed annually are considered Standard of Care.

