10. ADVERSE EVENT REPORTING

10.1 Adverse Events and Stopping Rules

Adverse events occurring during the enrollment period should be documented by the Investigator in progress notes, but will not be collected or analyzed by Indiana University School of Medicine unless considered serious by the Investigator. Adverse events will be reported according to federal guidelines for safety reporting for Investigational New Drug Application (IND).

Serious adverse events (SAEs) encountered during study enrollment will be documented by the Investigator and reported to Indiana University School of Medicine immediately upon discovery. SAEs are defined under current Good Clinical Practice (cGCP) guidelines as events that result in one or more of the following:

- life-threatening illness or injury;
- permanent impairment of a body structure or a body function;
- medically necessary in-patient hospitalization;
- medical or surgical intervention necessary to prevent permanent impairment to body structure or function; or
- fetal distress, fetal death, or congenital abnormality.

Serious events that affect the rights, safety, or welfare of subjects must be documented on a form and be reported immediately to Indiana University School of Medicine and to the Investigator’s IRB according to that IRB’s policies.

Major Adverse Cardiac Events (MACE). MACE endpoints will include: death, nonfatal myocardial infarction, including, Q-wave, non Q-wave, and CK/CKMB elevation, stroke, transient ischemic attack (TIA), hospitalization for heart failure, hospitalization for hypo or hypertension, life-threatening arrhythmia, and aneurysm rupture, which will be collected throughout the 6-month time period.

Severity Assessment. We will use the Common Terminology Criteria for Adverse Events (CTCAE), version 4.0, for detailed descriptions of Severity Grades. The CTCAE schema is classified by body system and event using the MedDRA hierarchy and provides descriptions of events that qualify under each severity rating.

The following table contains general descriptions of Adverse Event Severity Grades.

Severity Grade	Description
1	Mild. Asymptomatic or mild symptoms; clinical or diagnostic observations only; intervention is not indicated.
2	Moderate. Minimal, local, or non-invasive intervention indicated or limiting activities of daily living (i.e. preparing meals, shopping for groceries/clothes, managing money, using telephone, etc.)

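### No adverse-event contact is scheduled between discharge two hours after infusion and the Day 7 visit, nominally 166 hours; a scripted Day 1 call would bring first contact to about 22 hours

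*Combined protocol and SAP*

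**What the plan says.** Each patient receives one infusion. Section 6.1.4 describes what follows: "The patient will be observed for two hours after the study product infusion and then discharged home". It then says: "The patient will be re-examined on Days 7 and 14 for treatment related adverse events". Table 2, note 6, agrees on where monitoring stops: "Post infusion vital signs will be monitored at 15 min, 30 min, 1 and 2 hours". Note 7 ends pulse oximetry at the same point. Table 2 marks AE/SAE evaluations on Day 0 and next on Day 7 (plus or minus 2 days), with no column between.

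Section 7.1 contains one possible earlier contact. Product samples for "14-day bacterial sterility testing will be obtained". If a culture turns positive, "The PI will then notify the patient and the appropriate antibiotics will be started based on sensitivities of the identified organism", and a physical examination "will be conducted within 24 hours at which time a complete blood count will be obtained".

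Three other provisions bear on what an early contact would yield:

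- Section 3.4 makes the incidence of treatment-related adverse events over 24 months the primary safety endpoint.
- Section 10.1 says that adverse events during what it calls the enrollment period "will not be collected or analyzed by Indiana University School of Medicine unless considered serious by the Investigator". It does not define that period.
- Section 9 sorts events into three systems (cardiovascular, respiratory, infectious), while Section 11.1 names rash, mild fever and myalgia as the most notable risks.

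**The concern.** This is a Phase I trial of a single-dose allogeneic cell product, and treatment-related adverse events are its primary safety endpoint. The days just after infusion are a natural time to look for a delayed reaction, yet the schedule has no planned safety contact in them. A patient who becomes unwell at home on Day 1 or Day 3 is known to the study before Day 7 only if the patient calls, another provider reports the event, or a culture happens to turn positive.

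What is at stake is timeliness. A reaction that has resolved by Day 7 is dated from memory. One that has not resolved is acted on later than it could be. The stopping rules in Section 10.1 include single events (an embolic event suggesting ARDS, or one infusion-related death), so early discovery has practical value.

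The recording rules raise a second issue. If the enrollment period in Section 10.1 includes follow-up, its serious-only sentence contradicts the primary endpoint. Rash and myalgia have no system category in Section 9 in any case.

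**Working it through.** The plan states no gap in hours, so there is no figure to reproduce.

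**Inputs.** Discharge is 2 hours after infusion (6.1.4). The Day 7 visit falls on Day 5 to Day 9 (Table 2). The planned number of patients is 36 (5.1.1).

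**Assumptions.** The clock starts at the end of the infusion, and calls are made at hours 24 and 72.

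**Current plan.** Gap = visit day × 24 − 2.

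- Day 5: 120 − 2 = 118 h
- Day 7: 168 − 2 = 166 h
- Day 9: 216 − 2 = 214 h

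**With calls.** First contact is at 24 − 2 = 22 h (Day 1 call) or 72 − 2 = 70 h (Day 3 call). Day 1 to Day 3 is 48 h. Day 1 to Day 5/7/9 is 96/144/192 h. Day 3 to Day 5/7/9 is 48/96/144 h. The longest gap is the largest of the intervals in each schedule.

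| Schedule | First contact after discharge | Longest gap, visit on Day 5 / 7 / 9 |
|---|---|---|
| No call | 118 / 166 / 214 h | 118 / 166 / 214 h |
| Day 1 only | 22 h | 96 / 144 / 192 h |
| Day 3 only | 70 h | max(70, 48) = 70 / 96 / 144 h |
| Day 1 and Day 3 | 22 h | 48 / 96 / 144 h |

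The two calls do different work. The Day 1 call alone shortens the longest nominal gap by 166 − 144 = 22 h. The Day 3 call shortens it by 166 − 96 = 70 h, with or without a Day 1 call. The case for Day 1 is time to first contact, 22 h against 70 h.

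**Sensitivity.** If the clock starts at arrival and discharge comes at the end of the 4 to 6 hour Day 0 visit in Table 2, the gap to Day 7 is 168 − 6 = 162 h to 168 − 4 = 164 h. The gap to a Day 1 call is then 18 to 20 h. The conclusion does not change.

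**Is the culture-triggered contact a substitute?** It depends on a laboratory result, not on symptoms. Because the test runs 14 days, the result may come before or after Day 7. It is not a routine early contact.

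**Calls.** 36 × 1 = 36 for Day 1 alone; 36 × 2 = 72 for both days.

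**The case against.** The strongest reply is that no harm is shown. Section 11.1 calls the expected reactions mild and rare. Section 6.1.2 cites a trial of doses up to 5 million MSCs/kg without treatment-related events, and Section 9 says four earlier trials reported none. Events before Day 7 can be elicited at Day 7 and still count toward the 24-month endpoint. Table 2 as extracted also marks an infusion-reaction assessment at Day 14, and Section 10.1 requires serious events to be reported immediately on discovery. All of this stands as a limit on the benefit. None of it supplies a scheduled contact before Day 7.

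Section 6.1.4 also says that patients are admitted for continued observation, which might suggest a longer stay. The two-hour limit is explicit, however, and agrees with Table 2. Call-back instructions may exist in consent material outside the text reviewed, but they would not be scheduled contacts.

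A reader might go further than the documents allow in four ways:

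- **That early events are being missed.** The documents give no onset times or reaction rates, so this cannot be shown or sized.
- **That two calls are needed to shorten the longest gap.** A Day 3 call alone gives the same 96 h nominal figure. Day 2 and Day 4 calls would give max(46, 48, 72) = 72 h, so the choice of Day 1 and Day 3 is a judgement.
- **That the Day 7 window is certainly not binding.** Section 7.1 says "Window ranges for follow-up visits are guidelines for scheduling and will not be considered a protocol deviation", but this follows a sentence about long-term visits. Applying it to Day 7 is a fair reading, not a certain one.
- **That Section 10.1 plainly excludes non-serious events from follow-up.** That depends on what the enrollment period means. Table 2 schedules AE/SAE evaluations through Month 24, which points the other way.

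**Conclusion.** The point holds in a modest form. The schedule leaves 166 hours nominally between discharge and the next planned adverse-event contact, and 118 to 214 hours if the window is kept. The hours rest on the clock assumption above and are insensitive to it. An earlier contact would improve detection, dating and action on a delayed reaction. It cannot be claimed to correct a biased event rate. The change is worth making because the trial's main purpose is safety and the burden is small, although the documents give no costs or staffing figures to prove the latter.

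The Section 10.1 and Section 9 problems affect every visit and do not depend on the calls. The first is conditional on how the enrollment period is read. The second is not conditional: rash and myalgia fit none of the three listed systems.

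**What to change.** 1. In Table 2, add an AE/SAE evaluation by scripted telephone call on Day 1, and preferably another on Day 3. An existing nurse coordinator, who is blinded under Section 4.2, should make the calls rather than the unblinded PI, with identical questions in all three arms. The pre-infusion symptom list in Section 6.1.4 (fever, breathlessness, neurological change) is a ready start for the script.
2. In Section 10.1, state that non-serious adverse events after infusion are collected and analysed, and define the enrollment period.
3. In Section 9, add a system category for other events.

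Keep the two-hour observation and the Day 7 and Day 14 examinations as they are.

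The cost is 36 calls (Day 1 only) or 72 (both days) at full enrolment, a script, a CRF change, cover for calls that fall on weekends, and an IRB amendment. Recorded rates of mild events may rise in all arms. Edits 2 and 3 are wording changes and should be made even if the calls are declined.

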6.1.5 External studies

In the event that plans are made to conduct additional studies, new protocols describing the relevant handling, storage, accountability, and training procedures will be prepared specifically for those studies.

6.2 Other Study Materials

6.2.1 Materials to be provided by study site

- Study notebooks to maintain study documents, including signed ICFs, all applicable information, and additional forms to be collected and retained by the study institution during the course of the study.
- Example spreadsheets for tracking patient information.

6.2.2 Materials to be provided by external testing facilities

[figure not shown]
There are no external testing facilities associated with this study.

7. STUDY PROCEDURES

7.1 Workflow

MSC preparation. Donor infectious disease testing will be performed by CLIA certified Laboratories. Allogeneic donor Infectious Diseases testing will include anti-HIV-1/2 and anti-HCV. Testing will be repeated if it exceeds 30 days. Potential donors whose testing is incomplete or not available within 30 days will not be eligible to donate bone marrow and testing will be repeated to confirm ID markers. Potential donors testing positive for any of these infectious diseases will NOT be eligible.

Randomization Scheme and MSC Dosing. The PI, [name] MD., will determine inclusion in the study. After that decision has been rendered, the patient will be screened for enrollment. After enrollment, 36 patients will be randomized to receive MSCs or placebo IV through an antecubital vein (**Figure 1**).

Serum samples will be collected pre-MSD administration, 1 and 6 months' post MSC-treatment and analyzed in the Cellular Therapy Laboratory of University Hospital to determine if patients develop antibodies against allogeneic MSCs.

Baseline Screening and Follow-Up Schedule. The following evaluations will be carried out at baseline to determine if patient is eligible for study: (1) Baseline blood tests (complete blood count, serum chemistries and liver panel); (2) infectious disease panel and HLA typing; (3) medical history and physical exam; (4) concomitant medications; (5) pregnancy test for women of childbearing age ;(6)12 lead ECG; (7) 18-fluorodeoxyglucose (FDG) uptake with positron emission tomography/computed tomography (PET/CT) will be performed at baseline and Day 14. Computed tomographic angiography of the abdominal aorta and iliac arteries (as part of "Standard of Care") will be performed at month 12. Duplex ultrasound of the aorta will be performed at month 12 while the patients are enrolled in the trial to monitor AAA size. Follow up studies are detailed in **Table 2**, below. Subjects will return for long-term follow-up visits at six month intervals from year 1 (+/- 4 weeks) through year 5 (+/- 4 weeks). Window ranges for follow-up visits are guidelines for scheduling and will not be considered a protocol deviation if visits fall outside of these ranges. See **Table 3**, below, for details on the long-term follow-up visits.

- Annual CT abdominal exams beginning at year 1 are considered Standard of Care.

- MSCs products will be thawed and diluted 1:1 with Plasmalyte. Samples for cell viability (i.e. Trypan Blue and/or 7AAD) and 14-day bacterial sterility testing will be obtained. Viability >70% will need to be entered in the Certificate of Analysis before the product is released for administration.
- In the event of a positive sterility test result after products infusion, the physician and patient will be informed, and the results reported to the IRB and FDA. The positive result will be reported in an information amendment submitted to the IND in a timely manner, preferably within 30 calendar days after initial receipt of the positive culture test result (21 CFR 312.31).
 - Should cultures for detection of bacteria and fungi become positive, the Principal Investigator of the study will be notified. The PI will then notify the patient and the appropriate antibiotics will be started based on sensitivities of the identified organism.
 - A physical examination of will be conducted within 24 hours at which time a complete blood count will be obtained. Should there be an elevate white blood cell count (> 11.5K), the patient will be admitted to the hospital for intravenous antibiotics or antifungal medications. Should there be no clinical evidence of infection the patient will be treated for 7 days with oral antibiotics or anti-fungal medication
 - A systematic review of potential sources of contamination will be conducted with emphasis on skin preparation and draping and the components of the cell transport and preparation system. An examination of the sterile packaging for disposable components and the process of sterilization of non-disposable components will be performed as part of this review.
 - An infection as a result of contamination will be reported as an adverse event within 15 calendar

Table 2. Follow-Up Schedule

Procedures	Baseline	Day 0 MSC (4-6 hr. visit)⁹	Day 7 F/U (+/- 2 days)	Day 14 F/U (+/- 5 days)	Mo 1 F/U (+/- 1wk)	Mo 6 F/U (+/- 2wk)	Mo 12 F/U (+/-2 wk)	Mo 18 F/U (+/-2 wk)	Mo 24 F/U (+/-4 wk)
Informed Consent	X								
Medical History	X								
Physical Exam	X	X	X	X	X	X			
Vital Signs	X	X	X	X	X	X	X	X	X
Con. Medications	X	X	X	X	X	X	X	X	X
AE/SAE Evaluations	X	X	X	X	X	X	X	X	X
QoL Questionnaires	X					X	X	X	X
Infectious Disease Labs ¹	X								
Laboratory Evaluations	X ²				X ³				
12 Lead ECG	X ⁸				X				
Duplex Ultrasound	X					X	X	X	X
Randomization	X								
PET CT	X			X					
CT Angiogram ⁹							X		X
Blood Sample ⁴		X ⁵	X	X	X	X	X	X	X
Infusion Reaction Assessment ^{6,7}		X		X					

1. Infectious disease testing including basic HIV, Hepatitis C testing. HLA Typing will be performed at baseline, but is not exclusionary to enrollment, nor a protocol deviation if HLA results after study product infusion.
2. Baseline labs ONLY = CBC with differential, Glucose, Sodium, Potassium, Chloride, CO2, BUN, Creatinine, eGFR, hs-CRP, CPK, HbA1C, Total Bilirubin, Total Protein, Albumin, Alkaline phosphatase, alanine transaminase (ALT), aspartate transaminase (AST), platelet count, PT/INR, Pregnancy (childbearing Females-baseline only).
3. Follow-up labs = CBC with differential, Glucose, Sodium, Potassium, Chloride, CO2, BUN, Creatinine, eGFR, hs-CRP, CPK, Albumin, platelet count.
4. Peripheral blood draw for ancillary studies is up to 34 ml.
5. Day of MSC administration blood sample to be collected prior to study product infusion (can be done at physical exam if within 2 hours of infusion).

6. Infusion reaction assessment will include: clinical observation for signs of tachycardia and cutaneous flushing and vital signs (blood pressure, heart rate, respiratory rate, and temperature) at 15 min intervals throughout infusion starting 15 min prior to infusion. Post infusion vital signs will be monitored at 15 min, 30 min, 1 and 2 hours.
7. Oxygen saturation will be continuously monitored throughout infusion by pulse oximetry starting 15 min prior to infusion through 2 hours post infusion.
8. Baseline ECG may be obtained any time prior to study product infusion.
9. CT Angiograms beginning at year 1 and performed annually throughout subjects' participation are considered Standard of Care.

Table 3. Long-Term Follow-Up Schedule

	Mo 30 (+/-4wks)	Mo 36 (+/-4wks)	Mo 42 (+/-4wks)	Mo 48 (+/-4wks)	Mo 54 (+/-4wks)	Mo 60 (+/-4wks)
Duplex Ultrasound ¹	X	X	X	X	X	X
CT Angiogram ³		X		X		X
QOL Questionnaire	X	X	X	X	X	X
AE/SAE Evaluations	X	X	X	X	X	X
Blood Sample ²	X	X	X	X	X	X

1. Duplex ultrasound measured every six months is considered standard of care.

2. Peripheral blood draw for ancillary studies is 34 ml.

3. CT Angiograms performed annually are considered Standard of Care.

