	
 9. eGFR < 30mL/min. 10. Any condition requiring immunosuppressant medications (e.g., for treatment of organ transplants, psoriasis, Crohn’s disease, alopecia areata, rheumatoid arthritis, scleroderma, lupus). 11. Acute coronary syndrome in the last 30 days prior to enrollment. * 12. CHF hospitalization within the last 30 days prior to enrollment. * 13. HIV or HCV positive. 14. Contraindication to Computed Tomography or known allergy to contrast media. 15. Any bleeding diathesis defined as an INR ≥ 2.0 (off anticoagulation therapy) or history of platelet count less than 70,000 or hemophilia. 16. Pregnant or breast feeding women. 17. Significant hepatic dysfunction (ALT or AST greater than 2 times normal). 18. Life expectancy less than two years. 19. Inability to provide written informed consent due to cognitive or language barriers (interpreter permitted). 20. Presence of any clinical condition that in the opinion of the PI or the sponsor makes the patient not suitable to participate in the trial. 
*As defined by the standard definitions of CHF and ACS by the American Heart Association.

Participant Withdrawal Criteria	At the discretion of the investigator or at the request of the participant. The reason for withdrawal will be documented, specifically if the reason is due to an adverse event.

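### Scheduled safety labs occur once after infusion, at Month 1, without ALT, AST, alkaline phosphatase, bilirubin or CK-MB, so silent liver-enzyme change and silent early laboratory change have no scheduled test

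*Combined protocol and SAP*

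**What the plan says.** In section 7.1, the Table 2 row "Laboratory Evaluations" is marked at Baseline and at Month 1 (± 1 week) and nowhere else. Table 3, which covers Months 30 to 60, has no such row. The 12-lead ECG is likewise marked at Baseline and Month 1.

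Two footnotes define the panels. Footnote 2, which is limited to baseline, includes "Total Bilirubin, Total Protein, Albumin, Alkaline phosphatase, alanine transaminase (ALT), aspartate transaminase (AST), platelet count, PT/INR". Footnote 3 defines the later panel: "Follow-up labs = CBC with differential, Glucose, Sodium, Potassium, Chloride, CO2, BUN, Creatinine, eGFR, hs-CRP, CPK, Albumin, platelet count".

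ALT and AST also decide eligibility. Exclusion criterion 17 in Table 1 (section 5.3) reads "Significant hepatic dysfunction (ALT or AST greater than 2 times normal".

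Section 9 makes MACE a reported safety category. Section 10.1 includes in it "nonfatal myocardial infarction, including, Q-wave, non Q-wave, and CK/CKMB elevation", "which will be collected throughout the 6-month time period". CK-MB is on neither panel.

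On early visits, section 6.1.4 states: "The patient will be re-examined on Days 7 and 14 for treatment related adverse events". Table 2 marks a blood sample at both of those visits, and footnote 4 assigns it (up to 34 ml) to ancillary studies.

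**The concern.** Safety after a single infusion is the trial's principal question, and the primary safety endpoint is treatment-related adverse events over 24 months. Section 10.1 grades events by CTCAE, and its Grade 1 includes findings without symptoms that show only on a diagnostic test. A laboratory abnormality that the patient does not feel is therefore an adverse event under the plan's own definition. Such an event can be counted only if someone runs the test.

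Under the schedule as written, a report of no liver-enzyme events would be almost guaranteed, whatever the product does. The same applies to a blood-count, renal or CPK change that appears and resolves before Month 1. The safety profile would then look cleaner than the data allow, and section 3.4 intends this study to direct a Phase II trial.

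There is also a comparability problem. Without fixed panels, early tests are ordered on clinical suspicion, and section 4.2 leaves the principal investigator unblinded. Unscheduled testing could then differ by arm, whereas fixed panels would give the 12 placebo patients a like-for-like comparison.

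**Working it through.** The plan states no figure to reproduce here. The check sets the schedule, the panels and the endpoint definitions side by side.

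**1. How often safety labs are scheduled.** The follow-up visits after infusion are:
- Table 2: Day 7, Day 14, Months 1, 6, 12, 18 and 24 = 7 visits.
- Table 3: Months 30, 36, 42, 48, 54 and 60 = 6 visits.
- Total: 7 + 6 = 13.

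Safety labs fall at 1 of 13. They fall at 1 of 7 through Month 24, the primary safety horizon. Within the 6-month MACE period of section 10.1 (Day 7, Day 14, Month 1, Month 6) they fall at 1 of 4. Section 3.4 records MACE through year five; on that reading the fraction is again 1 of 13. Adverse-event review is marked at 13 of 13.

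**2. When the first one falls.** With a 28-day month the window opens at 28 − 7 = Day 21. With a 30-day month it closes at 30 + 7 = Day 37. Section 7.1 says that visits outside the windows are not deviations, so even this range is not binding.

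**3. What the panel drops.** Footnote 2 lists 21 items and footnote 3 lists 13, all of them also in footnote 2. The 21 − 13 = 8 dropped items are HbA1C, total bilirubin, total protein, alkaline phosphatase, ALT, AST, PT/INR and the pregnancy test. Of six liver-panel items (bilirubin, total protein, albumin, alkaline phosphatase, ALT, AST), five are dropped and albumin is kept. All 36 planned patients therefore have no scheduled ALT, AST, alkaline phosphatase or bilirubin after infusion in 60 months.

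**4. MACE wording against the panels.** Total CK (listed as CPK) is measured at Baseline and once afterwards, at Month 1. CK-MB is never scheduled. One CPK, three to five weeks after infusion, is the only scheduled enzyme test bearing on this component.

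**5. Other blood work.** Section 7.1 also provides anti-MSC antibody serum at Months 1 and 6, and a blood count if a product culture turns positive. Neither supplies a liver enzyme, and neither is a routine panel before Month 1.

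**6. How a zero would read.** Section 9 summarises incidence with 95% Wilson intervals. With no events in an arm of n, the upper limit is z²/(n + z²). For n = 12 and z = 1.96 this is 3.84/(12 + 3.84) = 24%. For both MSC arms together (n = 24) it is 3.84/27.84 = 14%. These limits assume that every patient was assessed. For liver enzymes, the number assessed by schedule is 0, so no such interval would be informative. This is an illustration only, since section 9 does not name a hepatic category.

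**The case against.** The best defence is that the split between a baseline panel and a shorter follow-up panel is deliberate. An eligibility test need not be repeated; HIV, hepatitis C and HbA1C are also baseline only. Section 9 names cardiovascular, respiratory and infectious systems, not hepatic, and plans no analysis of laboratory shifts. Section 11.1 names rash, mild fever and myalgia, and nothing in the documents points to a hepatic signal. The CK/CKMB wording describes a form of infarction and does not call for routine surveillance.

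Much of this stands, and it limits the point. A reader might infer that these toxicities have no visit able to detect them, or that the first three weeks are unobserved. The documents do not support either reading:
- Infusion takes place under telemetry and oximetry, with vital signs at 15-minute intervals.
- Patients are examined at Days 7 and 14, have a Day 14 PET/CT, and have adverse events reviewed at every visit.
- Nothing bars a test ordered on clinical grounds, and a symptomatic infarction can be recorded as an SAE or MACE.

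A reader might also infer that every liver test is dropped or that the CK/CKMB component is wholly unscheduled. Albumin is repeated, and total CK is measured at Month 1.

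What the defence does not supply is a scheduled ALT or AST after infusion, or any routine safety lab before Month 1. The primary endpoint covers treatment-related adverse events generally and is not confined to the three systems in section 9. Interview and examination cannot reveal a silent laboratory change.

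**Conclusion.** The point holds in a limited form. Symptomatic events can be captured. Silent change in ALT, AST, alkaline phosphatase or bilirubin has no scheduled test at any time after infusion, and silent change in the other analytes has none before about Day 21 to 37. CK-MB is unscheduled, so an enzyme-only event under the MACE definition rests on one CPK value. For these findings, an absence of events would mean not measured.

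This rests on reading the Table 2 marks by column position and on the schedule being followed exactly. Clinically driven tests would narrow the gap by an amount that cannot be known in advance, and possibly unequally across arms. No claim is made that the product harms the liver. The weakness is in ascertainment, it is cheap to correct, and the sponsor should correct it.

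**What to change.** 1. Add ALT, AST, alkaline phosphatase and total bilirubin to Table 2 footnote 3, so that each baseline value has a post-infusion counterpart. At Month 1 this needs no new visit or venepuncture: 36 × 4 = 144 extra results.
2. Preferably, also mark the follow-up panel at Day 7 and Day 14, where blood is already drawn: 36 × 2 = 72 more panels. With the Day 7 window of ± 2 days, the first planned safety lab would move from about Day 21–37 to Day 5–9. Allow a small volume beyond the ancillary draw, since the documents do not show that any of the 34 ml is spare.
3. Reconcile the CK/CKMB wording in section 10.1 with the two panels. Either CK-MB is run with the CPK, or the text states that CK/CKMB counts only when obtained for a clinical event. The choice is the sponsor's.
4. Reconcile section 10.1, which keeps non-serious events of the enrollment period out of the sponsor's collection and analysis, with the 24-month primary endpoint of treatment-related adverse events. The enrollment period is not defined there. If it covers follow-up, the added low-grade results would never be analysed and steps 1 and 2 would achieve little.
5. In the report, give the number of patients tested beside each laboratory event count.

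The cost is an amendment to Table 2, footnote 3 and section 10.1, modest laboratory charges, slightly more blood, and some extra low-grade findings to classify. These are changes in measurement and wording; they set no dose, treatment or stopping rule.
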